3.0 STUDY ENROLLMENT PROCEDURES AND PATIENT ELIGIBILITY

3.1 Study Enrollment

3.1.1 Patient Registration

Prior to enrollment on this study, patients must be assigned a COG patient ID number. This number is obtained via the COG Registry system once authorization for the release of protected health information (PHI) has been obtained. The COG patient ID number is used to identify the patient in all future interactions with COG. If you have problems with the registration, please refer to the online help.

In order for an institution to maintain COG membership requirements, every newly diagnosed patient needs to be offered participation in ACCRN07, *Protocol for the Enrollment on the Official COG Registry, The Childhood Cancer Research Network (CCRN)*.

A Biopathology Center (BPC) number will be assigned as part of the registration process. Each patient will be assigned only one BPC number per COG Patient ID. For additional information about the labeling of specimens please refer to the Pathology and/or Biology Guidelines in this protocol.

Please see [Appendix I](#) for detailed CTEP Registration Procedures for Investigators and Associates, and CTSU Registration Procedures including: how to download site registration documents; requirements for site registration, submission of regulatory documents and how to check your site's registration status.

3.1.2 IRB Approval

Sites must obtain IRB/REB approval for this protocol and submit IRB/REB approval and supporting documentation to the Cancer Trials Support Unit (CTSU) Regulatory Office before they can be approved to enroll patients. Allow 3 business days for processing. The submission must include a fax coversheet (or optional CTSU IRB Transmittal Sheet) and the IRB approval document(s). The CTSU IRB Certification Form may be submitted in lieu of the signed IRB approval letter. All CTSU forms can be located on the CTSU web page (<https://www.ctsuo.org>). Any other regulatory documents needed for access to the study enrollment screens will be listed for the study on the CTSU Member's Website under the RSS Tab.

IRB/REB approval documents may be faxed ([name]), E-mailed ([contact]) or mailed to the CTSU Regulatory office.

When a site has a pending patient enrollment within the next 24 hours, this is considered a "Time of Need" registration. For Time of Need registrations, in addition to marking your submissions as 'URGENT' and faxing the regulatory documents, call the CTSU Regulatory Helpdesk at: [name]. For general (non-regulatory) questions call the CTSU General Helpdesk at: [name].

Study centers can check the status of their registration packets by querying the Regulatory Support System (RSS) site registration status page of the CTSU members' web site by entering credentials at <https://www.ctsu.org>. For sites under the CIRB initiative, IRB data will automatically load to RSS.

Note: Sites participating on the NCI CIRB initiative and accepting CIRB approval for the study are not required to submit separate IRB approval documentation to the CTSU Regulatory Office for initial, continuing or amendment review. This information will be provided to the CTSU Regulatory Office from the CIRB at the time the site's Signatory Institution accepts the CIRB approval. The Signatory site may be contacted by the CTSU Regulatory Office or asked to complete information verifying the participating institutions on the study. Other site registration requirements (i.e., laboratory certifications, protocol-specific training certifications, or modality credentialing) must be submitted to the CTSU Regulatory Office or compliance communicated per protocol instructions.

3.1.3 Study Enrollment

Patient enrollment will be facilitated using the Oncology Patient Enrollment Network (OPEN). OPEN is a web-based registration system available on a 24/7 basis. To access OPEN, the site user must have an active CTEP-IAM account (check at < <https://eapps-ctep.nci.nih.gov/iam/index.jsp> >) and a 'Registrar' role on either the lead protocol organization (LPO) or participating organization roster.

All site staff will use OPEN to enroll patients to this study. It is integrated with the CTSU Enterprise System for regulatory and roster data and, upon enrollment, initializes the patient position in the Rave database. OPEN can be accessed at <https://open.ctsu.org> or from the OPEN tab on the CTSU members' side of the website at <https://www.ctsu.org>.

Prior to accessing OPEN, site staff and the results from the rapid central pathology screening review have confirmed the patient is eligible.

- All eligibility criteria have been met within the protocol stated timeframes.
- All patients have signed an appropriate consent form and HIPAA authorization form (if applicable).

Note: The OPEN system will provide the site with a printable confirmation of registration and treatment information. Please print this confirmation for your records.

Further instructional information is provided on the CTSU members' web site OPEN tab or within the OPEN URL (<https://open.ctsu.org>). For any additional questions contact the CTSU Help Desk at [name] or [contact].

3.1.4 Timing

Patients must be enrolled before treatment begins. The date protocol therapy is projected to start must be no later than five (5) calendar days after the date of study enrollment. **Patients who are started on protocol therapy on a Phase II study prior to study enrollment will be considered ineligible.**

Timing for enrollment will begin after the last definitive surgical intervention or clinical diagnosis. See [Section 3.2.5](#).

All clinical and laboratory studies to determine eligibility must be performed within 14 days prior to enrollment unless otherwise indicated in the eligibility section below.

3.2 Patient Eligibility Criteria

Important note: The eligibility criteria listed below are interpreted literally and cannot be waived (per COG policy posted 5/11/01). All clinical and laboratory data required for determining eligibility of a patient enrolled on this trial must be available in the patient's medical/research record which will serve as the source document for verification at the time of audit.

All clinical and laboratory studies to determine eligibility must be performed within 14 days prior to enrollment. Laboratory values need not be repeated if therapy starts within 14 days of obtaining labs to assess eligibility. If a post-enrollment lab value is outside the limits of eligibility, or laboratory values are >14 days old, then the following laboratory evaluations must be re-checked within 48 hours prior to initiating therapy: CBC with differential, bilirubin, ALT (SGPT) and serum creatinine. If the recheck is outside the limits of eligibility, the patient may not receive protocol therapy and will be considered off protocol therapy. Imaging studies must be obtained as outlined in [Section 3.2.3](#).

See [Section 7.1](#) for required studies to be obtained prior to starting protocol therapy.

INCLUSION CRITERIA

3.2.1 Age

Patients must be ≥ 3 years and ≤ 21 years at the time of study enrollment.

3.2.2 Diagnosis

Patients must be newly diagnosed with localized primary CNS NGGCT (Stratum 1) or localized primary CNS germinoma (Stratum 2). Germ cell tumors located in the suprasellar, pineal, bifocal (pineal + suprasellar) and ventricles are eligible. Tumors present in the above mentioned locations and with unifocal parenchymal extension are eligible. Please see exclusion criteria in [Section 3.2.6](#).

- Stratum 1 (NGGCT): Patients must have one of the following criteria.
 - Patients with serum and/or CSF hCG β > 100 mIU/mL or any elevation of serum and/or CSF AFP > 10 ng/mL or greater than

the institutional normal are eligible, irrespective of biopsy results.

- Patients with any of the following elements on biopsy/resection are eligible, irrespective of serum and/or CSF hCG β and AFP levels: endodermal sinus tumor (yolk sac), embryonal carcinoma, choriocarcinoma, malignant/immature teratoma and mixed GCT with malignant GCT elements
- **Stratum 2 (Germinoma):**
Patients must have both serum and CSF markers obtained (unless obtaining CSF is medically contraindicated) and must have one of the following criteria to be eligible.
 - Patients with institutional normal AFP (or ≤ 10 ng/mL if no institutional normal exists) in both serum and CSF (unless medically contraindicated) AND hCG β 5 - ≤ 50 mIU/ml in serum and/or CSF (unless medically contraindicated) (only 1 is required to be elevated) are eligible.. No histologic confirmation required.
 - Patients with bifocal (pineal + suprasellar) involvement or pineal lesion with diabetes insipidus (DI) AND hCG β ≤ 100 mIU/ml in serum and/or CSF AND institutional normal AFP (or ≤ 10 ng/mL if no institutional normal exists) in both serum and CSF (unless medically contraindicated) are eligible. No histologic confirmation required.
 - Patients with histologically confirmed germinoma or germinoma mixed with mature teratoma and hCG β ≤ 100 mIU/ml in serum and/or CSF and institutional normal AFP (or ≤ 10 ng/mL if no institutional normal exists) in both serum and CSF (unless medically contraindicated) are eligible..

Note: Patients who had more than one surgery/biopsy are eligible.

3.2.3 Imaging

Imaging studies must be obtained within 2 weeks prior to study enrollment.

Cranial MRI

All patients must have a cranial MRI with and without gadolinium at diagnosis/prior to enrollment. If surgical resection is performed, patients must have pre-operative and post-operative cranial MRI with and without gadolinium. The post-operative brain MRI should be obtained within 72 hours of surgery. If patient has a biopsy only, post-operative cranial MRI is recommended but not required.

Spinal MRI

All patients must have a spine MRI with gadolinium obtained at diagnosis/prior to enrollment.

Note: If the spine study is performed for the first time after surgical resection or biopsy, it is recommended to be obtained with and without gadolinium.

3.2.4 CSF

3.2.4.1 CSF Cytology

Lumbar CSF must be obtained prior to study enrollment unless medically contraindicated. If a patient undergoes surgery and lumbar CSF cannot be obtained at this time, then it should be performed at least 10 days following surgery before study enrollment. False positive cytology can occur within 10 days of surgery.

Note: Patients with positive CSF cytology obtained prior to 10 days after surgery may have cytology repeated to determine eligibility.

3.2.4.2 CSF Tumor Markers

Patients must have CSF tumor markers obtained prior to enrollment unless medically contraindicated. Ventricular CSF obtained at the time of CSF diversion procedure (if performed) is acceptable for tumor markers but lumbar CSF is preferred. In case CSF diversion and biopsy/surgery are combined, CSF tumor markers should be collected first.

3.2.5 Timing

Patients must be enrolled on ALTE07C1 prior to enrollment on ACNS1123.

Patients must be enrolled within 31 days of definitive diagnostic surgery (Day 0) or clinical diagnosis.

3.2.6 Organ Function Requirements

3.2.6.1 Adequate Bone Marrow Function Defined As:

- Peripheral absolute neutrophil count (ANC) $\geq 1,000/\mu\text{L}$
- Platelet count $\geq 100,000/\mu\text{L}$ (transfusion independent)
- Hemoglobin ≥ 8.0 g/dL (may receive RBC transfusions)

3.2.6.2 Adequate Renal Function Defined As:

- Creatinine clearance or radioisotope GFR ≥ 70 mL/min/1.73 m² or
- A serum creatinine based on age/gender as follows:

Age	Maximum Serum Creatinine (mg/dL)	
	Male	Female
2 to < 6 years	0.8	0.8
6 to < 10 years	1	1
10 to < 13 years	1.2	1.2
13 to < 16 years	1.5	1.4
≥ 16 years	1.7	1.4

The threshold creatinine values in this Table were derived from the Schwartz formula for estimating GFR (Schwartz et al. J. Peds, 106:522, 1985) utilizing child length and stature data published by the CDC.

3.2.6.3 Adequate Liver Function Defined As:

- Total bilirubin ≤ 1.5 x upper limit of normal (ULN) for age, and
- SGOT (AST) and SGPT (ALT) < 2.5 x upper limit of normal (ULN) for age.

3.2.6.4 Central Nervous System Function Defined As:

- Patients with seizure disorder may be enrolled if well controlled.
- Patients must not be in status, coma or assisted ventilation prior to study

enrollment.

EXCLUSION CRITERIA

3.2.7 Mature Teratoma

Patients with mature teratoma or completely resected immature teratoma with normal tumor markers are not eligible.

3.2.8 Tumors Outside Ventricles

Patients with tumors located outside the ventricles (basal ganglia, thalamus) are not eligible.

3.2.9 Metastatic Disease

Patients with metastatic disease by cranial or spinal MRI evaluation or CSF cytology (unless medically contraindicated) are not eligible.

3.2.10 Prior Therapy

Patients must not have received any prior tumor-directed therapy other than surgical intervention and corticosteroids.

3.2.11 Pregnancy and Breast Feeding

3.2.11.1

Female patients who are pregnant are ineligible.

3.2.11.2

Lactating females are not eligible unless they have agreed not to breastfeed their infants.

3.2.11.3

Female patients of childbearing potential are not eligible unless a negative pregnancy test result has been obtained.

3.2.11.4

Sexually active patients of reproductive potential are not eligible unless they have agreed to use an effective contraceptive method for the duration of their study participation.

REGULATORY

3.2.12

All patients and/or their parents or legal guardians must sign a written informed consent.

3.2.13

All institutional, FDA, and NCI requirements for human studies must be met.

4.0 TREATMENT PROGRAM

Timing of protocol therapy administration, response assessment studies, and surgical interventions are based on schedules derived from the experimental design or on established standards of care. Minor unavoidable departures (up to 72 hours) from protocol directed therapy and/or disease evaluations (and up to 1 week for surgery) for valid clinical, patient and family logistical, or facility, procedure and/or anesthesia scheduling issues are acceptable per COG administrative Policy 5.14 (except where explicitly prohibited within the protocol).

4.1 Overview of Treatment Plan

Induction Chemotherapy

All patients must begin therapy within 31 days of definitive diagnostic surgery or clinical diagnosis and 5 calendar days from enrollment on study. Each subsequent cycle of Induction chemotherapy will begin when ANC > 1,000/ μ L and platelets > 100,000/ μ L and when off filgrastim (G-CSF) for at least 48 hours (if applicable).

Cycle A: (21 Days)

Carboplatin (600 mg/m²/dose) Day 1
Etoposide (150 mg/m²/dose) Days 1-3

Cycle B: (21 Days)

Ifosfamide (1800 mg/m²/dose) Days 1-5
Etoposide (100 mg/m²/dose) Days 1-5
Mesna (1800mg/m²/day) Days 1-5
Filgrastim (G-CSF) (5 micrograms/kg/day) Days 6-15 or until ANC > 1500/ μ L

Growing Teratoma Syndrome

Second-look surgery is strongly recommended in patients with normalization of markers who fail to achieve a radiographic CR or PR to induction chemotherapy and in patients with increasing size of the mass on MRI scan and negative markers at any time during Induction chemotherapy. If a mature teratoma and/or fibrosis are removed, the patient remains on protocol and should continue therapy as planned. Response should be assessed according to the radiographic and tumor marker response criteria listed in [Section 10](#).

Chemotherapy for NGGCT (Stratum 1)

Week								
0	3	Evaluation	6	9	Evaluation	12	15	Response Evaluation
Cycle A	Cycle B	(MRI/tumor markers)	Cycle A	Cycle B	(MRI/tumor markers)	Cycle A	Cycle B	(MRI/tumor markers)

Patients will receive 6 cycles of induction chemotherapy consisting of carboplatin and etoposide (Cycles 1, 3, and 5) alternating with ifosfamide and etoposide (Cycles 2, 4, and 6). The entire length of Induction is approximately 18 weeks unless delay occurs due to myelosuppression or unanticipated toxicity.

Following induction chemotherapy, those patients in CR or PR will undergo radiation therapy 30.6 Gy WVI with IFR boost to 54 Gy in 1.8 Gy daily fractions.

For those patients with PR, SD or PD and normalization of tumor marker levels in serum and CSF, second-look surgery is strongly recommended. Patients who achieve CR/PR via second-look surgery (and have histology consistent with fibrosis, scar or mature teratoma) will then proceed to radiation therapy as above.

Patients with positive markers or who have < PR after induction chemotherapy/second-look surgery will be removed from protocol therapy.

Patients with residual viable malignant elements (except mature teratoma) on second-look surgery will be removed from protocol therapy.

Patients who are unable to undergo a second-look surgery due to safety or other reasons, will be taken off protocol therapy if they do not meet criteria for PR/CR (imaging and tumor markers).

Chemotherapy for Germinoma (Stratum 2)

Week					
0	3	Evaluation	6	9	Response Evaluation
Cycle A	Cycle A	(MRI/tumor markers)	Cycle A	Cycle A	(MRI/tumor markers)

Patients will receive 4 cycles of Induction chemotherapy consisting of carboplatin and etoposide. The entire length of Induction is 12 weeks unless delay occurs due to myelosuppression or unanticipated toxicity.

Following Induction those patients in CR/CCR will undergo radiation therapy (see guidelines below).

Patients with PR, SD with > 1.5 cm residual and PD with normalization of hCGβ should be considered for second-look surgery after completion of chemotherapy. Patients with evidence of new lesion(s) and/or increase in tumor markers will be removed from protocol therapy.

- If findings following (second-look) surgery are consistent with fibrosis, scar, mature teratoma or non-viable tumor, patients will receive 18 Gy WVI followed by 12 Gy boost to the primary site in 1.5 Gy daily fractions.

- If findings following (second-look) surgery indicate residual viable malignant elements, patients will be removed from protocol therapy.

Patients who have SD or PR with > 0.5 cm (suprasellar) or > 1 cm (pineal) but \leq 1.5 cm residual disease and do not undergo a second-look surgery due to safety or other reasons, will receive 24 Gy WVI followed by 12 Gy boost to the primary site in 1.5 Gy daily fractions.

- Patients who have SD or PR with greater than 1.5 cm residual tumor or PD but are unable to undergo a second-look surgery due to safety or other reasons, will be taken off protocol.

Radiation Therapy for NGGCT (Stratum 1)

Radiation therapy will be administered to all volumes in fractions of 1.8 Gy given once daily. See [Section 10.0](#) for response definitions.

- a. CR and PR: WVI to 30.6 Gy followed by IFR boost of 23.4 Gy to a total dose of 54 Gy.
- b. Stable disease (SD) or progressive disease (PD): Off protocol therapy unless a second-look surgery renders the patient in CR or PR.

Radiation Therapy for Germinoma (Stratum 2)

Radiation will be administered to all volumes in fractions of 1.5 Gy given once daily. See [Section 10.0](#) for response definitions.

- a. CR and continuous complete response (CCR): WVI to 18 Gy followed by local boost of 12 Gy to a total dose of 30 Gy.
- b. PR, SD and PD with normal markers: If (Second-look) surgery is consistent with no viable tumor or mature teratoma, WVI to 18 Gy followed by IFR boost of 12 Gy to a total dose of 30 Gy will be delivered. If any viable tumor (including Germinoma) is found, patients will come off protocol therapy.
- c. PR or SD with normal markers: Patients with > 0.5 cm suprasellar or > 1 cm pineal but \leq 1.5 cm residual who do not undergo second-look surgery will be treated with WVI to 24 Gy followed by local boost of 12 Gy to a total dose of 36 Gy. If second-look surgery is not performed and patients do not meet criteria for at least PR with \leq 1.5 cm residual disease, patients will be off protocol therapy.
- d. Progressive disease (PD): Patients with PD with normal serum and CSF markers after 4 cycles of chemotherapy will proceed to (second-look) surgery. If (second-look) surgery findings are consistent with mature teratoma or non-viable tumor, WVI to 18 Gy followed by IFR boost of 12 Gy to a total dose of 30 Gy will be delivered. Patients with any viable tumor (except mature teratoma) will be off protocol therapy. Patients with evidence of new lesion(s) and increasing markers or patients who do not have second-look surgery will be removed from protocol therapy.

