SD: Stable Disease
PD: Progressive Disease

See [Section 10](#) for specific radiographic and tumor marker definitions of CR, CCR, PR, SD and PD.

* Germinoma patients with PR, SD with > 1.5 cm residual and PD with normalization of hCGβ should be considered for second-look surgery. If histology confirms fibrosis, scar, mature teratoma or non-viable tumor, WVI to 18 Gy followed by local boost of 12 Gy to a total dose of 30 Gy will be delivered. Patients with > 0.5 cm (suprasellar) or > 1 cm (pineal) but ≤ 1.5 cm residual who do not undergo second-look surgery will be treated with WVI to 24 Gy followed by local boost of 12 Gy to a total dose of 36 Gy. If second-look surgery is not performed or patients do not meet criteria for at least PR with ≤ 1.5 cm residual disease or findings following second-look surgery indicate residual viable tumor, patients will be removed from protocol therapy.

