8.0 CRITERIA FOR REMOVAL FROM PROTOCOL THERAPY AND OFF STUDY CRITERIA

8.1 Criteria for Removal from Protocol Therapy

- a) Progressive disease with increasing markers during Induction chemotherapy.
- b) NGGCT (Stratum 1) patients with positive markers at the end of Induction chemotherapy or who have < PR after induction chemotherapy.
- c) NGGCT (Stratum 1) patients with < PR after second-look surgery or any viable tumor (except mature teratoma) after second-look surgery
- d) NGGCT (Stratum 1) patients who are unable to undergo second-look surgery due to safety or other reasons and do not meet criteria for CR/PR (imaging and tumor markers).
- e) Germinoma (Stratum 2) patients with PD and positive markers at the end of Induction chemotherapy.
- f) Germinoma (Stratum 2) patients who are unable to undergo second-look surgery due to safety concerns and they do not meet the criteria for at least PR with ≤ 1.5 cm residual disease without second-look surgery.
- g) Germinoma (Stratum 2) patients with any viable tumor (except mature teratoma, fibrosis, scar or non-viable tumor) after second-look surgery
- h) Refusal of further protocol therapy by patient/parent/guardian.
- i) Completion of protocol therapy.
- j) Physician determines it is in patient's best interest.
- k) Development of a second malignancy.
- l) Patient is enrolled but rechecked labs are outside the limits of eligibility prior to starting therapy. (See [Section 3.2](#))
- m) Radiotherapy cannot be initiated within 6 weeks after Day 1 of the last cycle of Induction chemotherapy or within 31 days after second-look surgery. (See [Sections 15.2.3](#) and [15.2.4](#)).
- n) Progressive disease with positive or increasing markers at the end of Induction chemotherapy, following second-look surgery or during radiation therapy.

Patients who are off protocol therapy are to be followed until they meet the criteria for Off Study (see below). Follow-up data will be required unless consent was withdrawn.

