10.3 Selection of Target Lesions

1. For most CNS tumors, only one lesion/mass is present and therefore is considered a “target” for measurement/follow up to assess for tumor progression/response.
2. In case of a bifocal lesion both lesions should be selected as “target” lesions.
3. The lower size limit of the target lesion(s) should be at least twice the thickness of the slices showing the tumor to decrease the partial volume effect (e.g. 8 mm lesion for a 4 mm slice).

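### Stratum 2 patients with less than a PR, residual tumor of 1.5 cm or less and no second-look surgery are given 36 Gy in one sentence and taken off protocol therapy in the next

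*Combined protocol and SAP*

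**What the plan says.** Section 4.1 covers this patient twice. Under chemotherapy for germinoma, patients with SD or PR and a residual above 0.5 cm (suprasellar) or 1 cm (pineal), up to 1.5 cm, who "do not undergo a second-look surgery due to safety or other reasons, will receive 24 Gy WVI" and a 12 Gy boost. Removal there goes by size: "Patients who have SD or PR with greater than 1.5 cm residual tumor or PD but are unable to undergo a second-look surgery" are taken off.

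Item c of the radiation text is headed for PR or SD with normal markers. Patients in the same size band "who do not undergo second-look surgery will be treated with WVI to 24 Gy followed by local boost of 12 Gy", for 36 Gy in total. The sentence after it reads "If second-look surgery is not performed and patients do not meet criteria for at least PR with" a residual of 1.5 cm or less, and ends in removal from protocol therapy.

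The same ground is covered elsewhere:

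- Section 15.1.2 gives SD or PR in this band a higher ventricular dose, then repeats the removal sentence.
- Section 15.2.4 sends PR or SD in this band to moderate-dose radiotherapy.
- The Schema 2 footnote sets the dose by size alone ("residual who do not undergo second-look surgery will be treated with WVI to 24 Gy followed by local boost of 12 Gy") and then removes ("If second-look surgery is not performed or patients do not meet criteria for at least PR with" the same limit).
- Section 8.1(f) removes patients who are "unable to undergo second-look surgery due to safety concerns and they do not meet the criteria for at least PR with" that limit.
- Section 15.6.3 sets 18 Gy plus 12 Gy by default. Its 24/36 Gy exception and table row name PR only, and its off-protocol row names SD or PD above 1.5 cm.
- Section 10.4 requires a residual above 1.5 cm in both SD definitions (3-D and 2-D).

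**The concern.** Dose in Stratum 2 depends on response (Section 15.0.1), so every patient needs one response category and one instruction. This patient has no category and two instructions. Two sites could treat identical children differently, one giving 36 Gy and the other ending protocol therapy, and each could cite the protocol. Section 15.11 scores a prescription as a major deviation when it differs by more than 10% from the protocol-specified dose, but here the specified dose is itself unclear.

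**Working it through.** **Patient traced.** Stratum 2, normal markers, less than PR but not PD, residual above the CR limit (>0.5 cm suprasellar, >1 cm pineal) but ≤1.5 cm, no second-look surgery. The sections below that name a response call this SD.

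**Instructions side by side.**

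| Place | Outcome for this patient |
|---|---|
| 4.1, chemotherapy for germinoma | 24 + 12 = 36 Gy |
| 4.1, item c, first sentence | 36 Gy |
| 4.1, item c, second sentence | Removed (less than PR) |
| Schema 2 footnote, dose sentence | 36 Gy, by size alone |
| Schema 2 footnote, next sentence | Removed |
| 15.1.2, dose sentence | Higher ventricular dose |
| 15.1.2, next sentence | Removed |
| 15.2.4, third bullet | Moderate dose |
| 8.1(f) | Removed, if surgery is not possible for safety concerns |
| 15.6.3, prose and table | Not named |

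The footnote goes further. It joins the absence of surgery and the failure to reach PR with *or*. Read literally, that removes even the PR ≤1.5 cm patients whom its preceding sentence irradiates.

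**Response category (10.4).** The residual exceeds the CR/CCR allowance. The decrease is below the PR threshold (65% by volume, 50% by area). Growth or new lesions sufficient for PD are absent. SD fails because the residual is not above 1.5 cm. The patient is therefore not CR, CCR, PR, SD or PD.

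**Is the group empty?** Assume one lesion that changes in proportion in every dimension, with baseline diameter b and residual r.

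- 3-D: not PR if 1 − (r/b)³ < 0.65, so b < r/0.35^(1/3). At r = 1.5 cm, b < 2.128 cm.
- 2-D: not PR if 1 − (r/b)² < 0.50, so b < r/0.50^(1/2). At r = 1.5 cm, b < 2.121 cm.
- Example: 1.8 cm to 1.4 cm is a volume decrease of 1 − (1.4/1.8)³ = 52.9% and an area decrease of 1 − (1.4/1.8)² = 39.5%. This is below PR by either rule, and 1.4 cm is too small for SD.

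The group is not empty, but it needs a small baseline lesion. The calculation does not bound bifocal disease or irregular shrinkage. No firm lower limit follows. Section 10.3 says "The lower size limit of the target lesion(s) should be at least twice the thickness of the slices showing the tumor", which is 0.8 cm for its 4 mm example and 1.0 cm for the 5 mm maximum that Section 15.5.3 allows for diagnostic MR.

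**Dose difference if 15.6.3 alone were followed.** Ventricular: (24 − 18)/24 = 25.0%, or 16 versus 12 fractions of 1.5 Gy. Total: (36 − 30)/36 = 16.7%, or 24 versus 20 fractions. The boost is 12 Gy either way.

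**Design figures.** None is disputed. For Stratum 2, the exact binomial rule of at least 73 of 79 gives type I error 0.0978 at 0.87 and power 0.8999 at 0.95, in line with the stated 0.10 and 90%.

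**The case against.** The best defense is that the intent can be found. Four places name SD or PR up to 1.5 cm for the higher dose, and the footnote does so by size. The Section 4.1 chemotherapy text limits removal of SD or PR to residuals above 1.5 cm, and the off-protocol row of Table 15.6.3 agrees for SD. The removal sentences could then be loosely worded remainder clauses. This is probably what was meant, and the fix adopts it. It does not clear the text: the PR test in item c, Section 15.1.2 and the footnote does not say so, and Section 8.1(f) is the formal removal list.

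The group is also small. Second surgery is highly recommended in Section 15.1.2, so few such patients may go without it. That limits the size of the problem and does not resolve the conflict.

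A reader might infer a third outcome, 18 Gy ventricular and 30 Gy total, from the default in Section 15.6.3. No sentence assigns that dose to SD. It arises only if Section 15.6.3 is read alone, against Sections 15.1.2 and 15.2.4 in the same chapter. The on-treatment review in Section 15.10.1 could also catch it: the ventricular plan is due within three days of starting, with post-chemotherapy imaging when there was no second surgery. That review would not catch a wrongful removal.

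**Conclusion.** The treatment rule is internally inconsistent and wrong as written. For this patient the main consequence is 36 Gy versus removal from protocol therapy. The conflict rests on the current text alone. The 2.13 cm figure also assumes proportional change in a single lesion. The documents give no count of such patients, and none is estimated here.

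A reader might infer that the conflict distorts the 3-year PFS test, because Section 9.1 selects patients by receipt of dose-reduced radiation. The documents do not support a figure for that: the group is uncounted, and Section 9.2.3 projects the evaluable patients from CR or CCR only. No effect on type I error, power or sample size is claimed. The point should be fixed, because the ambiguity concerns a child's radiation treatment and the remedy is cheap.

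**What to change.** Apply the size rule in the Section 4.1 germinoma chemotherapy text throughout, once the study committee confirms that 36 Gy and not removal is intended.

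1. **Section 10.4, both SD definitions.** Replace the requirement of more than 1.5 cm with a residual above the CR limit (>0.5 cm suprasellar, >1 cm pineal). This section serves both strata. Stratum 1 handling does not change, because removal there rests on less than PR.
2. **Item c, Section 8.1(f), Section 15.1.2 and the Schema 2 footnote.** Replace the test of PR with ≤1.5 cm by: *patients without second-look surgery are removed for PD, residual >1.5 cm, or positive markers*. In the footnote, change the *or* after *not performed* to *and*. Keep the removals for viable tumor.
3. **Section 15.6.3.** In both prose bullets and the 24/36 Gy row, write: *PR or SD with residual above the CR limit and ≤1.5 cm, no second-look surgery*. Limit the 18/30 Gy default to CR/CCR or benign findings at second-look surgery. Change the off-protocol row to: *viable tumor at second surgery; or no second-look surgery with PR or SD >1.5 cm or any PD; or positive markers*. Match the headings of Tables 15.9c and 15.9d.

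The three changes to the doses and rows in item 3 belong together. Rewording the 24/36 Gy exception alone would let PR above 1.5 cm without surgery fall to the literal 18/30 Gy default, and would leave PD ≤1.5 cm without surgery with no row.

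The cost is an amendment of wording and the committee's confirmation. No procedures or patients are added, and no design figure changes.
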